2.3 RISK/BENEFIT ASSESSMENT

2.3.1 KNOWN POTENTIAL RISKS

Physical risk

Voxelotor: The most common adverse reactions reported with incidence > 10% are headache, diarrhea, abdominal pain, nausea, fatigue, rash, and pyrexia. No significant toxicities requiring medical intervention have been reported. If a subject complains of intolerable side effects, voxelotor will be stopped and the subject will come off study. Voxelotor binds to hemoglobin. When the drug is stopped, voxelotor-modified hemoglobin will degrade, and no long-term risk is expected.

CPET: Aggravation of SCA symptoms during exercise testing is unlikely, because exercise testing is stopped when participants complain of fatigue or discomfort. Studies of exercise testing in patients with sickle cell disease have been published, including GBT's phase 1/2 voxelotor study, and no adverse events, such as pain crisis, have been reported.^{8, 13, 14-17, 24}

Venipuncture: The risks of drawing blood from a vein include fainting, local pain, bruising, swelling, or rarely an infection at the needle site. Patients routinely have blood draws as part of regular sickle cell care, and this study will take blood from the same venipuncture as routine care blood draws, no extra venipunctures are required. In the event of adverse effects to the subjects, necessary medical or professional intervention will be instituted immediately. Approximately 5 cc (1 teaspoon) of blood will be drawn for study labs on 2 occasions in the study.

Psychological risk

Voxelotor treatment: Most patients are already taking the medication for sickle cell disease. Adding another oral medication to be taken at the same time as the existing medication is unlikely to induce an adverse psychological effect.

CPET: Patients may experience potential anxiety, stress, and uncomfortable emotions if CPET results are not as they expected. As we do not know what the expected peak VO₂ will be for our patient population, we have no expected results for peak VO₂ and will not be communicating any expectations to our patients that might be anxiety-provoking. CPET will be explained to patients and patients will be prepared for CPET by the exercise physiologist to reduce apprehension and anxiety. A pediatric psychologist is part of the sickle cell care team and is available to provide counseling, if needed.

Venipuncture: Blood draw is part of routine sickle cell care. This study will obtain blood from the same venipuncture used for routine blood work, therefore will post no additional psychological effect.

Economic risk

Patients and/or their parents will be compensated for participation and their travel costs to the exercise lab will be covered by the study, therefore there is no economic risk.

Legal risk

There is no legal risk.

Social risk

Privacy will be maintained. There is no foreseeable social risk.

2.3.2 KNOWN POTENTIAL BENEFITS

Immediate direct benefits of study participation to the patients include free access to the newly FDA approved medication voxelotor, rise in hemoglobin and improved oxygen carrying capacity, as well as free exercise testing that can provide information for personal physical activity guidelines.

Long-range benefits include fewer complications of sickle cell disease and potentially improved lifestyle.

2.3.3 ASSESSMENT OF POTENTIAL RISKS AND BENEFITS

Voxelotor has proven benefit in sickle cell disease without toxicity. CPET has been shown to be safe for sickle cell patients. The risk of minor adverse reactions to voxelotor is significantly outweighed by the benefit of higher hemoglobin, decreased sickling, and fewer sickle cell complications. The information gained from this study about exercise capacity, which is a functional outcome of the new medication (rather than just a blood test result), greatly outweighs the inconvenience of trips to the exercise lab.

3 OBJECTIVES AND ENDPOINTS

| OBJECTIVES | ENDPOINTS | JUSTIFICATION FOR ENDPOINTS |
|--|---|--|
| Primary | | |
| Compare peak VO ₂ from sequential CPETs performed on SCA patients before and during voxelotor therapy | Change in Peak VO ₂ from baseline to Week 8 (voxelotor) | The gold standard for exercise capacity is peak VO ₂ . |
| Secondary | | |
| Correlate peak VO ₂ with biochemical markers, including hemoglobin, reticulocyte count, bilirubin, lactate dehydrogenase, haptoglobin, hemoglobin F, % F cells, P50 oxygen dissociation, point of sickling. | Correlation of peak VO ₂ with biochemical markers of sickling and hemolysis | These are established measurements of the biochemical effects of sickling and hemolysis. They will show whether improved exercise capacity is a direct or indirect effect of voxelotor's biochemical activity. |
| Tertiary/Exploratory | | |
| HRQOL assessment | Clinician Global Impression of Change and Patient Global Impression of Change assessments (CGIC and PGIC) | The small number of patients on this pilot study may limit CPET quantitative results from reaching statistical significance. Whether or not peak VO ₂ changes significantly on voxelotor, whether voxelotor has the potential to offer overall clinical improvement and better quality of life can be assessed. |

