1 PROTOCOL SUMMARY

1.1 SYNOPSIS

Title:

The Effect of Voxelotor on Exercise Capacity of Youths with Sickle Cell Anemia

Study Description:

This study is a pilot, open-label, single-arm study to evaluate the effect of voxelotor on exercise capacity, as measured by cardiopulmonary exercise testing (CPET) in patients 12 years of age and older with sickle cell anemia (SCA). Voxelotor was recently approved for the treatment of SCA in patients 12 years and older. We hypothesize that exercise capacity will be improved by voxelotor treatment in sickle cell patients whether they are on Hydroxyurea or not. This study will assess exercise capacity by cardiopulmonary exercise testing (CPET) before and after 8 weeks of voxelotor therapy.

Objectives:

Primary Objective: To evaluate the effect of voxelotor on peak oxygen consumption (VO₂) in adolescents with SCA as assessed by change in CPET from baseline.

Secondary Objective: To correlate peak VO₂ with biochemical markers, including hemoglobin, reticulocyte count, bilirubin, lactate dehydrogenase, haptoglobin, % Hgb F expressing cells, P50 oxygen dissociation, point of sickling (POS), and dense cells.

Exploratory Objective: To evaluate the effect of voxelotor on HRQOL as assessed by patient-reported outcome (PGIC) and clinician-reported outcome (CGIC) at end of treatment study visit

Endpoints:

Primary endpoint: Change in Peak VO₂ from baseline

Secondary endpoint: Hemoglobin and biochemical markers of sickling and hemolysis

[figure not shown]
Exploratory endpoint: Clinician and Patient Global Impression of Change assessment (CGIC and PGIC)

Study Population:

1.1.1.1.1 Patients seen in the Pediatric Sickle Cell Program in Northern Virginia (Fairfax, VA) who have a genetically severe forms of sickle cell disease (including Hgb SS, Hgb Sbeta⁰thalassemia, or Hgb SC^{Harlem}) and are age 12 or older.

| | |
|--|--|
| Phase: | This is a single-center, open-label, single-arm longitudinal interventional pilot study. |
| Description of Sites/Facilities Enrolling Participants: | The outpatient sickle cell clinic of Pediatric Specialists of Virginia located in the Schar Cancer Institute on Inova Hospital Campus in Fairfax, VA. This pilot study aims to enroll 10 patients. |
| Description of Study Intervention: | During the open-label treatment period, all participants will receive voxelotor at a fixed dose of 1500mg (administered as three 500mg tablets) orally once daily for 8 weeks |
| Study Duration: | 12 months |

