1.2 SCHEMA

1.3 SCHEDULE OF ACTIVITIES (SOA)

| Procedures | Screening/ Enrollment Day -60 | Study Visit 1 Day -30 +/- 7 days | Study Visit 2 Day - 29 to -1 | Study Visit 3 Day 1 +/- 14 days | Study Visit 4 Day 30 +/- 7 days | Study Visit 5 Day 60 +/- 7 days | Study Visit 6 Day 60-89 | Final Study Visit 7 Day 90 +/- 14 days |
|--|-------------------------------------|--|------------------------------------|---------------------------------------|---------------------------------------|---------------------------------------|----------------------------|---|
| Informed consent | x | | | | | | | |
| Demographics | x | | | | | | | |
| Medical history | x | | | | | | | |
| Dispense voxelotor ^d | | | | x | x | x ^d | | |
| Concomitant Medication review | x | x | | x | x | x | | x |
| Physical exam | x | x | | x | x | x | | x |
| Vital signs, Ht, Wt | x | x | x | x | x | x | x | x |
| Performance status | x | | | | | x | | x |
| Routine labs ^a | x | x | | x | x | x | | x |
| Study labs ^b | | x | | | | x | | |
| Pregnancy test ^c | x | | | x | x | x | | |
| Adverse event review and evaluation | x | | | x | x | x | | x |
| Schedule CPET | | x | | | | x | | |
| CPET | | | x | | | | x | |
| CGI, PGI assessments | | | | | | | | x |
| Data collection and entry | x | x | | x | x | x | | x |

^a Routine labs: CBC diff, retic, CMP, LDH, haptoglobin, Hemoglobin F or hemoglobin electrophoresis

^b Study labs: Send to UCSF [name] lab: % F cells, P50 oxygen dissociation, ektacytometry, point of sickling (POS), dense cells.

^c Pregnancy test: All menstruating female participants

^d Participants will be treated with voxelotor for at least 8 weeks before the 2nd CPET, which will be scheduled as close to the date following 8 weeks of treatment with voxelotor. Participants will continue voxelotor until the 2nd CPET is completed.

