8 STUDY ASSESSMENTS AND PROCEDURES

8.1 EFFICACY ASSESSMENTS

Efficacy of study drug will be assessed as follows:

- CPET (cardiopulmonary exercise test) is non-invasive and will be performed using a motorized treadmill (Trackmaster Model TMX428, Full Vision, Inc.). Participants will have their nose clipped and breathe through a mouthpiece with a nonbreathing valve. Breath by breath gas exchange data will be collected and analyzed using a VMax Encore 29C metabolic cart (CareFusion Corp, San Diego, CA). The participants will have EKG leads and pulse oximetry monitoring while running on a treadmill that increases in incline incrementally to induce peak physical effort according to a modified Bruce protocol based on patient age, size, and exercise ability. A peak exercise response will be defined as a respiratory exchange ratio of greater than 1.1 or to patient's volitional fatigue. The patient exercises for 8-12 minutes. Approximately 1.5 hour will be allotted for the entire CPET visit, which will include checking in, explanation of the procedure, preparation and setup for the test, the exercise test itself, and post-test debriefing. This exercise test will be done twice by each participant: once before and once after starting the study drug. The CPET report will be provided to the participant.
- During exercise the following will be measured and recorded:
 - · 12-Lead ECG
 - · Pulse oximetry
 - · Blood Pressure
 - · Peak HR
 - · Peak VO₂ (ml/kg/min)

- · Peak VO₂ (L/min)
 - · Respiratory Exchange Ratio (RER)
 - · O₂ Pulse
 - · VE/VO₂
 - · VE/VCO₂
 - · VO₂/HR
 - · VAT (ventilatory anaerobic threshold)
 - · Percent VO₂ at VAT
- Blood will be drawn for study labs once before the study drug and once after. Study labs will be performed by the research laboratory of [name] at UCSF. Blood samples will be sent by FEDEX overnight.
 - Blood work as part of regular standard of care will continue to be done during the study.
 - The “Patient Global Impression of Change” and the “Clinician Global Impression of Change” single-question surveys will be completed by the participant and the clinician, respectively, at the final study visit.

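### PGIC and CGIC are rated only after the second CPET, and nothing keeps its peak VO2 result from the raters until they have rated

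*Protocol*

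**What the plan says.** **Timing of the ratings.** The Schedule of Activities (section 1.3) has one row, "CGI, PGI assessments", with a single mark at Final Study Visit 7, Day 90 +/- 14 days. Section 8.1 agrees: the "single-question surveys will be completed by the participant and the clinician, respectively, at the final study visit". The synopsis (section 1.1) is looser and places the "clinician-reported outcome (CGIC) at end of treatment study visit".

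**Timing of the second CPET.** The Schedule puts it at Visit 6, Day 60-89. Footnote d adds a second CPET "which will be scheduled as close to the date following 8 weeks of treatment with voxelotor", with voxelotor continued until that test is done.

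**Release of the result.** Section 8.1 lists among the contents of the CPET visit "the exercise test itself, and post-test debriefing" and then states: "The CPET report will be provided to the participant". Section 5.5 promises each participant a full report. Section 2.3.1 lists distress over unexpected CPET results as a psychological risk, so participants are expected to learn them. Section 10.1.9.1 gives the principal investigator and study personnel access to the database. Section 6.3, on minimising bias, says only that it does not apply because there is no randomization.

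**Purpose of the ratings.** Section 3 first notes that few patients may keep the CPET results from reaching significance. It then describes what the global impressions can still show: "Whether or not peak VO ₂ changes significantly on voxelotor, whether voxelotor has the potential to offer overall clinical improvement". Quality of life is named there as well. Section 9.4.9 plans no exploratory analyses.

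**The concern.** Section 3 gives the global impressions a fallback role: they are to say something about clinical benefit when the peak VO2 comparison is inconclusive. They do that best when they reflect how the participant feels and how the clinician finds the participant, not the CPET number itself.

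Each rating is one question about change. If the rater already knows that peak VO2 went up or down, that knowledge can shape the answer. Section 9.4.2 specifies one peak VO2 measurement before drug and one on drug, so the observed change in any participant includes test-to-test noise. A rating influenced by the reported change would carry some of that noise. A reader of the individual listings (section 9.4.8) could then take agreement between the ratings and peak VO2 as two lines of evidence when one partly derives from the other. Section 9.4.1 says the pilot is meant to help justify a larger trial, so such a reading could have some influence. No later analysis can undo disclosure that came before the rating.

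**Working it through.** The plan gives no figure on this point. The check is visit-window arithmetic and a reading of the relevant sections side by side.

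**1. Order of events**
- Visit 6 (second CPET): Day 60 to 89.
- Visit 7 (PGIC and CGIC): nominal Day 90; window 90 - 14 = Day 76 to 90 + 14 = Day 104.
- Gap at nominal Day 90: 90 - 89 = 1 day to 90 - 60 = 30 days.
- Largest gap: 104 - 60 = 44 days.
- Smallest gap on windows alone: 76 - 89 = -13 days, so the windows overlap on paper. The visits are numbered in sequence, and footnote d ties the CPET closely to completion of eight weeks of treatment. The planned order is therefore CPET first, ratings second.

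**2. Can the participant know the result by then?** A debriefing forms part of the CPET visit, and a full report goes to every participant. Section 2.3.1 presumes that participants learn their results. No release date is given, and no passage makes release wait for the ratings. Knowledge before rating is possible and not prevented. It is not documented as certain.

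**3. Can the clinician know it?** The protocol does not say so directly. It follows by inference from study-team access to the database (10.1.9.1), the open-label design (4.1) and the absence of any rule separating the CGIC rater from the CPET data. The Schedule marks data entry at Visit 7 but not at Visit 6, so the date on which the second result reaches the database is not fixed either.

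**4. Is there a safeguard elsewhere?** Sections 1.1, 1.3, 2.3.1, 3, 5.5, 6.3, 8.1 and 10.1.9 contain none.

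**5. Where could the ratings go instead?** On the Schedule, Visit 5 (Day 60 +/- 7) has physical examination, medication review, performance status, laboratory tests and adverse event review. It is also the visit at which the second CPET is scheduled, so it precedes that test. Visit 6 has only vital signs and the CPET marked. Section 8.2 says in general terms that all visits include an examination and laboratory tests, which the Schedule does not bear out for Visit 6. A CGIC at Visit 6 check-in would therefore have no clearly scheduled clinical assessment behind it.

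**6. Size.** The quantity that matters is the share of ratings moved by knowledge of the result. The protocol gives nothing to estimate it from, so the range is 0 to 100%.

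**The case against.** The other side has four fair arguments.

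**Disclosure is not stated as fact.** A reader might infer that every participant has been told whether peak VO2 rose or fell before rating. The protocol does not support that: the content of the debriefing, the date of the report and the clinician's access are all left open. What stands is the weaker statement that the raters may know and nothing prevents it.

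**Section 3 does not claim independence.** A reader might take it to promise ratings separate from, or blind to, the CPET. The sentence before the quoted one concerns statistical significance in a small sample, and the section makes no claim of independence. What stands is that the fallback role is weakened if the ratings partly repeat the CPET result.

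**There is bias anyway, and little depends on it.** Participants and clinicians know the treatment, routine blood counts are taken at Visits 3, 4 and 5, and participants feel their own effort on the treadmill. Withholding one report would not turn the ratings into unbiased evidence of drug benefit. No comparison of the ratings with peak VO2 is planned. This stands in full and is why the point is minor. It does not remove the case for a near-free safeguard, because this source of bias, unlike open-label expectation, can be avoided.

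**The bias cannot be sized.** One might offer a chance calculation: with an inert drug and no order effect, 5 of 10 participants are expected to have a higher second peak VO2, and 7 or more do so with probability (120 + 45 + 10 + 1)/1024 = 176/1024 = 17%. That describes how readily peak VO2 moves by chance. It does not show how far the ratings would follow, so it is no measure of the bias.

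**Conclusion.** The point holds as a minor one. The documents establish that both ratings are planned only after the second CPET, by 1 to 30 days at nominal Day 90 and by up to 44 days at the edges of the windows. They also establish that the result goes to participants and that no rule keeps it from either rater beforehand. The effect on the ratings is possible, of unknown size, and additional to the unavoidable expectation bias of an open-label, single-arm study. It is confined to an exploratory endpoint for which section 9.4.9 plans no analysis. A reader might infer that the primary result is compromised; it is not, since peak VO2 is measured before the ratings are made.

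The conclusion rests on two assumptions: that visits take place in their numbered order, and that the CGIC rater is among the study personnel with access to the data.

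**What to change.** State in section 8.1, with a footnote to the Schedule, that PGIC and CGIC are completed before either rater is given the second CPET result. Either of two arrangements would do:

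- **Keep Visit 7.** Withhold the second CPET report, and any discussion of its peak VO2 at the debriefing or in clinic, until both forms are signed. Safety findings from the test are passed on at once. The cost is a later report: 1 to 30 days after the test at nominal Day 90, at most 44.
- **Move to Visit 5.** The forms then precede the second CPET and nothing has to be withheld. The cost is a somewhat earlier rating, nominally Day 60 instead of Day 90.

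Visit 6 check-in is the weaker choice, because the Schedule marks no clinical assessment there to support a CGIC.

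In the same edit, reconcile the synopsis, which ties the ratings to the end of treatment, with the Schedule and section 8.1, which place them at a final visit after the second CPET, up to which footnote d has voxelotor continue. Neither arrangement adds a visit, a test or a patient, and every participant still receives the promised report.

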4 STUDY DESIGN

4.1 OVERALL DESIGN

Hypothesis: Voxelotor improves exercise capacity in SCA patients.

Study type: single-center, open-label, single-arm longitudinal interventional pilot study

Methods: Patients with genetically severe forms of sickle cell disease age 12 or older will be enrolled from the PSV sickle cell clinic in Northern Virginia. A baseline CPET will be performed. Voxelotor will be initiated, and a second CPET will be performed. The CPET after the study intervention (voxelotor) will be compared to the baseline CPET. Each patient will be his/her own control.

4.2 SCIENTIFIC RATIONALE FOR STUDY DESIGN

The phenotype of sickle cell anemia is variable, depending on genetic modifiers, such as baseline fetal hemoglobin level, and response to the existing sickle cell therapy Hydroxyurea. The baseline hemoglobin in sickle cell anemia patients vary; individuals' physical activity also vary, whether they have sickle cell disease or not, and CPET results would likely show significant inter-subject variability across the sickle cell population. To answer the question whether voxelotor increases exercise capacity for individual patients taking the drug, inter-subject variability can be eliminated by comparing each subject to him/herself. In addition, fewer subjects will be needed in a longitudinal design than if subjects were divided into a study group and a control group. Therefore, we chose a longitudinal design, in which each participant's CPET after voxelotor is compared to the same participant's CPET before initiation of voxelotor.

4.3 JUSTIFICATION FOR DOSE

The dose of 1500 mg daily for voxelotor is the standard approved dose, as a result of dose comparison studies completed and published by GBT.

4.4 END OF STUDY DEFINITION

A participant is considered to have completed the study if he or she has completed all phases of the study including 2 CPETs and the last visit shown in the Schedule of Activities (SoA), Section 1.3.

5 STUDY POPULATION

5.1 INCLUSION CRITERIA

Subjects will be recruited from the Pediatric Specialists of Virginia Sickle Cell Program.

In order to be eligible to participate in this study, an individual must meet all of the following criteria:

1. Provision of signed and dated informed consent form
2. Stated willingness to comply with all study procedures and availability for the duration of the study
3. Male or female, age \geq 12 years
4. In good general health as evidenced by medical history and diagnosed with a genetically severe form of sickle cell anemia (Hgb SS, Hgb S beta 0 thalassemia, Hgb SC^{Harlem}, and others)

5. Patients who are on Hydroxyurea need to be on a stable dose for at least 3 months without anticipated change in dosing until the study is completed.
6. Ability to take oral medication and willingness to adhere to daily voxelotor and 2 CPETs at scheduled intervals.
7. For females of reproductive potential who are sexually active: use of highly effective contraception for at least 1 month prior to screening and agreement to use such a method during study participation and for an additional 30 days after the end of study.
8. For males of reproductive potential: use of condoms or other methods to ensure effective contraception with partner

5.2 EXCLUSION CRITERIA

An individual who meets any of the following criteria will be excluded from participation in this study:

1. Patients on chronic transfusions or who received a transfusion within last 8 weeks
2. Patients who had hospitalization for vaso-occlusive crisis or acute chest syndrome within 30 days prior to informed consent/assent.
3. Patients who have screening alanine aminotransferase (ALT) > 4X upper limit of normal
4. Patients who suffer from physical inactivity attributable to clinically significant musculoskeletal, cardiovascular, or respiratory comorbidities
5. Patients already taking commercially available voxelotor
6. Prior hypersensitivity to voxelotor or excipients.
7. Pregnant patients

